6.8.3 Follow-Up for Subjects Withdrawn from Treatment

Subjects will be followed on an intention-to-treat basis; data from all enrolled subjects who are assigned a participant identifier and who undergo islet transplantation will be collected, irrespective of outcome, for the scheduled minimum follow-up period of one year.

6.9 Adverse Events Definitions and Monitoring

6.9.1 Adverse Event (AE)

An adverse event is any unfavorable and unintended diagnosis, symptom, sign (including an abnormal laboratory finding), syndrome, or disease which either occurs during the study, having been absent at baseline, or if present at baseline, appears to worsen.

The length of time between screening and first transplantation may be 6 months or more. Therefore, non-serious adverse events will be recorded on the case report forms (CRF) for the period starting with hospitalization for the first transplantation and during the subsequent study period because these events are relevant to the islet cell transplantation. All serious adverse events (see below) regardless of time relative to transplantation will be recorded on the case report form

6.9.2 Serious Adverse Event (SAE)

A serious adverse event (experience) is defined (21 CFR 312.32) as any adverse experience that suggests a significant hazard, contraindication, side effect, or untoward medical occurrence that:

1. Results in death
2. Is life-threatening
3. Requires or prolongs hospitalization, including emergency room care
4. Causes persistent or significant disability or incapacity
5. Results in congenital anomaly
6. Requires intervention to prevent permanent impairment or damage or in the judgment of the investigator represents significant hazard to the study participant.

6.9.3 Assessment of Causality

The relationship or attribution of a medical event or toxicity, or a serious adverse event (being possibly related or not) to an investigational product or therapy represents the best estimate of the principal investigator or sub-investigator at the time of reporting the causal relationship.

The investigator's determination of treatment-relatedness (attribution) for each medical event or toxicity should be recorded in the source documentation and on the case report form. For this protocol, the investigator must place the attribution in either the "possibly related" or "not possibly related" categories. (This collapses the five suggested NCI-CTC categories—definite, probable, possible, unlikely, and unrelated—into a binary choice of possibly related or not.). For each event, the attending physician or clinician in

Version 0031 8/7/14

conjunction with the research nurse who examined and evaluated the subject should assign the attribution. Data managers who are removed from the clinical assessment of the subject must not perform this important task.

6.9.4 Severity of Adverse Event

Severity grades are assigned by the investigator to indicate the severity of medical events and toxicities. This protocol will use the Collaborative Islet Transplant Consortium *Terminology Criteria for Adverse Events (TCAE) In Trials of Adult Pancreatic Islet Transplantation, Version 5.0 (03 August 2011)* for reporting and grading medical events. The purpose of using the TCAE system is to provide a standard language to describe toxicities and medical events in islet transplantation, to facilitate tabulation and analysis of the data, and to facilitate the assessment of the clinical significance of treatment-related toxicities and medical events.

- The TCAE provides a detailed list of terms and a grade that closely describe the medical event or toxicity. While over 300 terms are described, each with a graded severity scale, the investigator may need to insert new terms when an applicable term cannot be found in the list.

Adverse events *not* included in the TCAE listing should be recorded and graded 1 to 5 according to the *General Grade Definitions* provided below (see Table 1):

Table 1. General Grade Definitions for Items Not in TCAE Listing

Grade	Descriptor	Definition
1	Mild	Transient or mild discomforts (< 48 hours), no or minimal medical intervention/therapy required, hospitalization not necessary (non-prescription or single-use prescription therapy may be employed to relieve symptoms, e.g., aspirin for simple headache, acetaminophen for post-surgical pain)
2	Moderate	Mild to moderate limitation in activity; some assistance may be needed; no or minimal intervention/therapy required, hospitalization possible
3	Severe	Marked limitation in activity, some assistance usually required; medical intervention/therapy required, hospitalization possible
4	Life-Threatening or Disabling	Extreme limitation in activity, significant assistance required; significant medical/therapy intervention required, hospitalization or hospice care probable
5	Death	Death

6.9.5 Monitoring and Reporting Adverse Events

The investigator will monitor participants for the occurrence of adverse events during the course of the study. In addition, a Data Monitoring Committee (DMC) will assist in the

monitoring of patient safety (see Section 6.12.2). All non-serious adverse events reported from the time of hospitalization for the initial islet cell transplantation and subsequent study period will be recorded on the case report form. All serious adverse events regardless of time relative to transplantation will be recorded on the case report form. The investigator will instruct subjects prior to transplantation to report any physical changes or new symptoms that they notice during the course of the study.

Physicians and health care personnel involved in the subject's medical care will be instructed to report all serious adverse events (defined above) as soon as possible to:

[name]
Associate Professor of Surgery
University of Illinois
[name]
[name]
[contact]
Email: [contact]

When a serious adverse event is considered reportable to regulatory agencies, [name] will prepare the initial report and forward copies to the FDA, the Institutional Review Board (IRB), and the Data Monitoring Committee. Under FDA regulations (21 CFR 312.32) the sponsor of an IND application, in this case the investigator, is required to report in writing within 15 days to the FDA any serious and unexpected adverse experiences, and by telephone and facsimile within 7 days any unexpected fatal or life-threatening event. For reporting events to the FDA, an FDA3500-Medwatch form will be filled out and submitted to the appropriate authorities with copies to the UIC IRB.

According to monitoring procedures in place at University of Illinois at Chicago, the investigator must report all deaths, clinically significant infections, and hospitalizations, regardless of potential association with the investigational therapy to the IRB. Other serious adverse events and toxicities are also submitted to the IRB.

Serious events will be followed until resolved or considered stable. The following attributes must be assigned: description, date of onset and resolution (if known when reported), severity, assessment of relatedness to test therapy, and action taken.

According to institutional procedures at the study site, outcomes of serious adverse events are also reported to the IRB throughout the study period. Regular updates at scheduled visits include completion of the toxicity grading, which should reflect the status (improvement, stability, or worsening) of each adverse event reported. When requested, the investigator must summarize in writing the details regarding remarkable adverse events, their treatment and resolution for review by the IRB and relevant regulatory authorities.

All transplant procedure related complications are reviewed on a weekly morbidity and mortality meeting within the Department of Surgery at the University of Illinois at Chicago and supervised by the Chief of General Surgery at UIC.

The principal investigator and co-investigators will apply their clinical judgment whether or not an adverse event is of sufficient severity to require that the subject should immediately be removed from treatment related to the transplantation (e.g., subsequent islet transplantation, immunosuppressive therapies, etc.) (see Section 6.9 *Subject Withdrawal or Discontinuation*). If necessary, the investigator must suspend any trial treatments and institute any necessary medical therapy to protect a subject from any immediate dangers. Review of safety events by ethics review committee or IRB, or the FDA or relevant local regulatory authorities may also suspend further trial treatments.

A subject may also voluntarily withdraw from treatment due to what he/she perceives as an intolerable adverse event or for any other reason. If voluntary withdrawal is requested, the subject should be asked to continue (at least limited) scheduled evaluations, complete an end-of-study evaluation, and be given appropriate care under medical supervision until the symptoms of any adverse event resolve or his/her condition becomes stable.

Reporting of Pregnancy

Subjects of childbearing potential, both male and female, must be either surgically sterile or use adequate contraception and express an intent not to become pregnant while participating in this study. For participants who are not surgically sterile, investigators will recommend contraception methods using either a) hormonal and barrier method combination, or b) abstinence (for both male and female subjects).

Documentation that counseling was provided regarding the importance of contraception during participation in the study will be recorded in the subject's medical chart.

Pregnancy occurring while the subject is participating in this study will be reported to the IRB and measures taken as described in Section 6.9 *Withdrawal or Discontinuation*.

6.9.6 Enrollment and Transplantation Stopping Rules

The investigator will stop study enrollment and islet transplantation in the event that the following events occur:

- 2 subjects experience hepatic vein thrombosis following transplantation, or
- 3 final islet preparations show positive culture results, or
- 1 subject experiences death related to the procedure

In addition, the DMC will review eligibility and safety data through 2 weeks after transplantation and agree that islet transplantation can continue with the next subject (see Section 6.12.2).

The study investigator will notify the FDA and IRB that enrollment and transplantation have been stopped. Transplanted subjects will continue to be monitored for safety and efficacy and continue to receive immunosuppressive therapy to maintain their transplants. The investigators and DMC will review all safety data on all subjects enrolled as well as safety data on subjects experiencing these events. These data and assessments of the investigator and DMC will be submitted to the IND for FDA review

and discussion. Enrollment will resume and the 2nd or 3rd islet cell transplantation be conducted only when the FDA has reviewed the clinical safety data and notified the investigator that the procedure can continue.

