If access to the portal vein cannot be gained by transvenous or transcutaneous approach, the subject will be brought to the operation theatre. A small laparotomy will be performed under local or general anesthesia, and portal access will be gained through cannulation of a mesenteric vein (24-26). The surgery will be performed by the PI, [name], or a co-investigator.

The islet preparation may consist of fractions of different purity with a total packed cell volume of less than 10 mL. If the total packed cell volume of the islet preparation is greater than 5 mL, the lot will be divided into two sub-lots during the purification process so that the higher purity fractions may be pooled separately from lower purity fractions and labeled accordingly. Each sub-lot will be divided into syringes (or bags) each containing a maximum of 1 mL of total packed islet cells (if syringes are used). If more than one sub-lot of the islet preparation is to be administered (i.e., where sub-lots are identified as having different islet purity), the lot with the higher purity will be administered first. Mixing sub-lots together for simultaneous administration is not permitted.

The islets will be injected slowly (each syringe over a period of at least 5 minutes) by [name] or a co-investigator. During the injection, the syringe is turned constantly to avoid sedimentation of the islets and clumping. If the bag system is used, the islets are infused by gravity.

Portal pressure will be monitored before and after infusion of one syringe load (50 mL volume containing 1 mL of tissue). Any change in portal pressure will be documented, and if the intra-portal pressure rises above 22 mmHg, infusion of subsequent syringes must be held until the pressure falls below 18 mmHg. If the bag system is used, the portal pressure is taken intermittently, and if the intra-portal pressure rises above 22 mmHg, the infusion must be held until the pressure falls below 18 mmHg. The bag

system must be repetitively and gently shaken to keep the islet preparation in suspension and avoid clumping.

Following each infusion, if the portal pressure remains elevated above 22 mmHg for longer than 10 minutes, then no further infusion will be administered through the hepatic vein, and the procedure will be terminated.

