The procedure, duration of injection, number of syringes injected and discarded, and portal pressures will be recorded in the case report form. Also, any adverse event occurring during the transplant process will be recorded in the case report form.

After successful completion of the islet infusion, the catheter and syringe or bag system will be rinsed with an additional 20 mL of transplant media, which is infused through the cannula over approximately 2 minutes, and a final portal pressure documented. Under ultrasound or fluoroscopic guidance with very minimal further contrast use, the sheath tip is withdrawn from the main portal vein into the liver parenchyma. Contrast media (iodinated contrast or if allergic, CO₂ or gadolinium) is used to confirm extraportal position of the sheath. While the subject continues to be monitored, Avitene microfibrillar collagen hemostat (BARD, Davol Inc., Warwick, RI) paste mixed with diluted contrast is injected into the sheath to seal the liver parenchymal tract. Under fluoroscopic guidance the sheath is withdrawn while injecting the Avitene paste until the sheath is removed and Avitene paste seals the liver parenchymal tract to the peripheral portal vein. Alternatively, the catheter is withdrawn slowly over 30 minutes or more, allowing formation of an autologous blood clot. The catheter is then removed completely and the subject returns to the Transplant Unit with instructions to lie recumbent for 4 hours. Abdominal ultrasound and Doppler examination of the liver are performed the day after the procedure to exclude procedure related complications such as portal vein thrombosis or intra-abdominal bleeding (see Section 6.6.6 and Appendix *Post-Transplant Orders*).

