6.6.6 Early Post-Transplant Period (see Appendix Post-Transplant Orders)

After the islet transplant procedure, subjects will stay for a minimum of 24 hours in hospital with close monitoring in the UIC Hospital Transplant Unit (7W), offering intensive care unit equivalent conditions. Vital signs are monitored every 15 minutes for the first hour, then every 30 minutes for 4 hours, then every 4 hours thereafter until discharge. During the first 24 hours after islet transplantation, liver tests, amylase, lipase, and CBC will be monitored every 8 hours.

Starting at least 4 hours after the islet infusion, subjects will begin a series of treatments with low molecular weight heparin (enoxaparin sodium, Lovenox® 30 mg sc bid, which may be self-administered) for seven days. Hemoglobin will be monitored 3 times during the first week following the transplant procedure.

An ultrasound and Doppler evaluation of the portal system will be performed within 24 hours after each islet transplantation procedure to rule out the possibility of complication including portal thrombus or perihepatic hematoma. If portal vein thrombosis is encountered within a main right or left portal branch within the main portal vein (i.e., main portal vein, but not a segmental peripheral branch), this will be considered a serious adverse event (SAE). In case of portal thrombosis, the subject will receive therapeutic anticoagulation with heparin until reaching a therapeutic INR with oral anticoagulants for a period of 3 months. Ultrasound will be repeated until the portal vein thrombus is resolved.

Subjects will be discharged home 24 hours after transplant if afebrile, having stable hemoglobin, and provided post-transplant Doppler ultrasound is within normal limits. Subjects will be provided with contact information in the event of questions or adverse experiences following discharge.

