6.10.1 Safety

Safety of islet cell transplantation in Type 1 diabetes depends primarily on determining the incidence of serious and unexpected complications or adverse events. Additionally, the ability of the cell isolation laboratory to produce uncontaminated islet cell preparations with minimal endotoxin content will be considered as a safety variable. The surgical implantation procedure has associated risk and complications of the islet cell infusion will be followed closely. The post-transplant immunosuppression regimen also has expected toxicities, both acute and chronic. Laboratory measures and signs and symptoms will be followed at specified intervals (see Section 6.6.8 *Schedule of Evaluation* and Appendix *Detailed Visit Schedule*). Some of these measures are often more subjective and variable in nature, but should provide a clear indication of relative safety for subjects enrolled in this study.

All study participants who receive an islet cell transplant will be followed for safety for 1 year following the last transplantation. The safety of the islet transplantation and associated immunosuppressive therapies will be evaluated by analysis of adverse experiences, clinical laboratory tests, and physical examination. Safety events will be analyzed by their incidence, severity, and relationship to islet cell transplantation. In particular, the following parameters are of primary interest in assessing the clinical safety of islet cell transplantation:

Specification of Safety Parameters

One year after first and the last islet transplants we will evaluate:

- a. Procedure Related Events
The incidence and severity of adverse events related to the islet infusion procedure including:
 - Bleeding (> 2 g/dl decrease in hemoglobin concentration)
 - Portal vein thrombosis, branch or main
 - Biliary puncture
 - Wound complication (infection or subsequent hernia)
 - Increased transaminase levels (> 5 times upper level of normal)
- b. Immunosuppression Related Events

The incidence and severity of adverse events related to immunosuppression including allergy:

- Reduction in GFR (> 25% reduction in estimated GFR from baseline by Cockcroft and Gault formula)
- Increase in urinary albumin excretion
- New onset microalbuminuria (albumin > 30 mg/day confirmed by 24 hour urine collection) in patients who were previously within normal limits

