6.11.2 Patient Eligibility and Safety

Data Monitoring Committee

In order to assist in the monitoring of the safety of subjects participating in this study, the investigator will establish a Data Monitoring Committee (DMC). The DMC will consist of 3 members who have training in medicine and/or organ transplantation. Some members may provide temporary coverage for the investigator or co-investigator while they are off-site (e.g., vacation) but otherwise will not be involved in the medical care of subjects. In the event that a DMC member is covering an investigator, that member will reclude him/herself from voting on DMC decisions. At all times, only one member may cover an investigator at a time so that 2 members are available for review of safety data and to make any decisions.

For each subject, the DMC will review the eligibility and safety data approximately 2 weeks following each islet cell transplantation. In the event that a second transplantation will be done in the same subject during the first 2 weeks following the first transplantation, the DMC will review the eligibility and available safety data for this subject prior to his/her second transplantation. The DMC must review the safety data through week 2 following transplantation on the preceding subject and agree that islet cell transplantation can continue in the subsequent subject. In this way, an interval of 2 or more weeks will exist between subjects undergoing islet transplantation to allow the review of safety events. This applies to the first 2 subjects in this cohort. If no serious events were observed, subsequent transplants can be performed in another patient during this 2-week review phase following a transplant.

The DMC will meet every 3 months to review the collected clinical data in order to assess safety. The DMC may also meet in an emergency situation when requested by the investigators or should the study meet a stopping rule (See Section 6.10.6).

It should be noted that in addition to the formal monitoring of safety by the DMC, the IRB will be notified of each serious adverse event. As described above, the IRB has the right to suspend the clinical study at any time for safety reasons.

Subject Eligibility

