9.3.4 Enoxaparin (Lovenox®)

Enoxaparin is an FDA approved low molecular weight heparin that will be given for the prophylaxis of portal vein thrombosis for a duration of seven days after islet transplantation. Known adverse effects include bleeding and thrombocytopenia. See Appendix *Package Insert Lovenox®*.

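### The stopping rule counts hepatic vein thrombosis, but the thrombosis the protocol monitors is portal, so non-fatal portal vein thromboses never trigger the automatic halt

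*Protocol*

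**What the plan says.** Section 6.9.6 of the Protocol has three automatic stopping criteria: "2 subjects experience hepatic vein thrombosis following transplantation", three culture-positive final islet preparations, or one procedure-related death. After a halt, transplantation resumes "only when the FDA has reviewed the clinical safety data" and the investigator has been told that it may continue.

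Elsewhere, wherever a thrombosed vein is named, it is the portal vein:

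- **Imaging.** Section 6.5.1 orders abdominal ultrasound and liver Doppler the day after the procedure "to exclude procedure related complications such as portal vein thrombosis or intra-abdominal bleeding". Section 6.6.6 requires a Doppler study of the portal system within 24 hours of every transplant.
- **SAE status.** Section 6.6.6 makes portal vein thrombosis an SAE, treated with three months of anticoagulation. It limits the SAE to the "main portal vein, but not a segmental peripheral branch"; the sentence also names the right and left branches.
- **Safety parameter.** Section 6.10.1 lists "Portal vein thrombosis, branch or main" among the procedure-related events. SAP Sections 2.7.1 and 10.1.5 repeat it.
- **Prophylaxis.** Section 9.3.4 gives enoxaparin "for the prophylaxis of portal vein thrombosis".
- **Known risk.** Section 9.1.2 names bleeding and portal vein thrombosis as the complications of the transhepatic injection.

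Section 6.5.3 also mentions thrombosis of the liver as a reason for heparin, without naming a vein. The hepatic vein otherwise appears as part of the transvenous access route (Protocol 3.1.3 and 6.5.1, SAP 2.5.1). It also appears in the portal-pressure paragraph of 6.5.1, where a persistent rise means "then no further infusion will be administered through the hepatic vein".

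**The concern.** A stopping rule protects participants because it fixes in advance which events halt the study. Here the event in the rule differs from the event the study looks for. Hepatic vein thrombosis has no definition, is not a listed safety parameter and is not the stated target of any scheduled test. Portal vein thrombosis has all three, and it is absent from the rule.

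The structure of the trial adds weight to this. Section 6.9.5 makes the investigator the IND sponsor, and 6.9.6 makes the investigator the person who stops the study. Written criteria matter most when those roles coincide. The slip also carries into DMC activity: under 6.11.2 an emergency meeting follows an investigator request or a met stopping rule, and for portal events the second route is closed.

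Substituting one word would leave a second question open. Section 6.6.6 excludes segmental peripheral branches from SAE status, while 6.10.1 and SAP 10.1.5 count branch events. The investigator and the DMC could reasonably disagree about whether 2 had been reached.

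**Working it through.** **Step 1: test a non-fatal portal vein thrombosis against each criterion in 6.9.6.**

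| Criterion | Met by a non-fatal portal vein thrombosis? |
|---|---|
| 2 subjects, hepatic vein thrombosis | No, different vein |
| 3 culture-positive preparations | No |
| 1 procedure-related death | No, by definition non-fatal |

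The contribution to the automatic halt is 0 whatever the event rate. This needs no assumption.

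**Step 2: what the criterion would do if it named portal vein thrombosis.** The plan gives no operating characteristics for the rule, so there is no stated figure to reproduce. Inputs:

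- n = 50 subjects (Protocol 4.4 and 6.3, planned minimum)
- trigger at X ≥ 2 affected subjects (6.9.6)
- p = probability that a subject has at least one qualifying event over all infusions. No planning value is given, so 1% to 10% is assumed.

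Exact binomial: P(X ≥ 2) = 1 − (1 − p)^n − n·p·(1 − p)^(n−1).

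For p = 0.02 and n = 50: 1 − 0.98^50 − 50 × 0.02 × 0.98^49 = 1 − 0.364 − 0.372 = 0.264.

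SAP Section 2.8 also discusses power with as few as 15 patients, so smaller sizes are shown.

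| Assumed p | n = 15 | n = 20 | n = 50 |
|---|---|---|---|
| 1% | 0.010 | 0.017 | 0.089 |
| 2% | 0.035 | 0.060 | 0.264 |
| 5% | 0.171 | 0.264 | 0.721 |
| 10% | 0.451 | 0.608 | 0.966 |
| Any p, rule as written, non-fatal portal events | 0 | 0 | 0 |

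**Step 3: effect of the event definition.** Suppose main, right or left portal thrombosis ran at 1% and the wider definition including branches at 5%, both purely for illustration. At n = 50 the choice of definition would move the trigger probability from 0.089 to 0.721.

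**The case against.** The strongest reply is that other safeguards cover the gap. Section 6.9.6 itself adds that the DMC reviews two-week safety data and agrees before the next subject is transplanted. Under 6.11.2, "The DMC will meet every 3 months to review the collected clinical data in order to assess safety", and it can meet in an emergency. Main, right or left portal thrombosis is an SAE reported to the IRB. Procedure complications go to a weekly morbidity and mortality meeting, and the IRB, the FDA or the investigator can suspend treatment (6.9.5). A fatal case meets the death criterion. All of this stands and limits the likely harm. None of it is an automatic halt, however, and 6.11.2 applies the two-week hold to the first two subjects, relaxing it afterwards if no serious events were seen. Whether a later SAE would restore that hold is unclear from the text.

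A second reply is that the hepatic vein may have been meant. The transvenous route passes a sheath through it, so thrombosis there is conceivable, the liver Doppler could detect it, and the 6.5.1 portal-pressure sentence could be literally true for that route. That is fair: a drafting slip is likely but remains an inference, and 6.5.1 calls for clarification more than correction. It does not explain why the monitored complication is missing from the rule, and the percutaneous route does not use the hepatic vein.

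Third, an SAE definition narrower than the tabulated category is ordinary and not in itself a contradiction. Agreed. It matters here because a corrected rule has to choose one. It is also right that the probabilities fall at smaller n and describe how often a corrected rule would pause the trial, not patient harm.

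**Conclusion.** The concern holds, with high confidence, and should be fixed. As written, non-fatal portal vein thromboses contribute nothing to the automatic halt in 6.9.6, and the requirement for FDA review before restart does not attach to them. That conclusion rests on the text alone. What is lost is the pre-specified, non-discretionary trigger; reporting and discretionary review remain. The size of the difference a corrected rule would make depends on the unknown event rate: 9% to 97% chance of a halt in 50 subjects across assumed rates of 1% to 10%, and 1% to 45% in 15.

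**What to change.** Amend 6.9.6 so that the thrombosis criterion is portal vein thrombosis in 2 subjects after transplantation, with hepatic vein thrombosis kept as an additional event if it was intended. State which definition the count uses: the 6.6.6 SAE definition (main, right or left portal vein, segmental peripheral branches excluded) or the 6.10.1 definition that includes branches. Ask the clinical team and DMC to confirm that 2 is the right count under that definition. In the same amendment, clarify the reference to the hepatic vein in the portal-pressure paragraph of 6.5.1, so that it is correct for both access routes.

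The cost is a short protocol amendment and notice to the DMC, with no new procedures or patients. The downside is a greater chance of a pause: about 26% over 50 subjects if the true rate is 2%, and 72% if it is 5% (assumed rates).
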